7.2.1 Demography

Age at inclusion (years)

Patient's age will be a derived variable, defined in years according to the formula: Age = (date of signature of written informed consent—date of birth) / 365.25.

- Sex (Male/Female)
 - If Female, Childbearing potential assessed (Yes / Not done / NA)
 - If Not done, reason

CER-001-CLIN-009 CER-001

 If Yes, Childbearing potential (Childbearing potential with contraceptive protection / Uncertain childbearing potential or post-menopausal status / Surgically sterilized / Post-menopausal)

- If Childbearing potential with contraceptive protection, method(s) of contraception
- If Yes, FSH value (IU/L)
- If Yes, Pregnancy test result (Negative/Positive/NA)
- Race (Caucasian / Asian / Black or African American / American Indian or Alaska native / Native Hawaiian / Other pacific island / Other / NA)
 - o If Other, specification
- Ethnicity (Hispanic/Non-Hispanic/NA)

7.2.2 Medical history and concomitant diseases

Medical history and concomitant diseases will be assigned to the Lowest Level Term (LLT), and a Preferred Term (PT) will be classified by a High Level Term (HLT), a High Level Group Term (HLGT) and a System Organ Class (SOC) according to the Medical Dictionary for Regulatory Activities (MedDRA) thesaurus, version 19.1.

Concomitant diseases will be defined as all diseases/conditions which are ongoing at screening visit. All others will be considered as medical history.

Concomitant diseases and medical history will be summarized according to the Table 2 template (*Cf.* Section 12.2) as follows:

- Number and percentage of patients presenting at least one event (medical history / concomitant disease)
- Number and percentage of patients presenting at least one event (medical history / concomitant disease) tabulated by SOC and PT

7.2.3 Risk factors

- Smoking status (Smoker / Former smoker / Non-smoker)
 - If Smoker, Current daily consumption (cigarettes/day)
 - If Former smoker, time since smoking cessation (< 1 year / Between 1-5 years / > 5 years)

7.2.4 Patient profile

- Cardiovascular disease background (Symptomatic/Asymptomatic)
 If Symptomatic:
 - History of cardio or cerebrovascular events (Yes/No)
 - Diagnosed coronary artery disease (Yes/No)
 - Diagnosed carotid or peripheral stenosis (Yes/No)
 - Previous myocardial revascularisation percutaneous coronary intervention, or coronary artery bypass graft (Yes/No)

If Asymptomatic, imaging methods used for diagnosis:

- Doppler ultrasound (Yes/No)
- B-mode ultrasonography (Yes/No)
- Intravascular ultrasonography (Yes/No)
- Computed Tomography (Yes/No)
- Magnetic Resonance Imaging (Yes/No)

7.3 Treatment exposure and compliance

7.3.1 Treatment exposure

Duration of treatment exposure (weeks) will be described on the safety population according to the actual treatment received. It will be calculated as follows:

Duration of treatment exposure (weeks) = (Date of last infusion - Date of first infusion + 1) / 7

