## **6.6 Safety extension protocol**

Patients having completed their last infusion 48 weeks after the first one will be offered to continue in the study for 6 months for safety follow-up.

All patients who accept to continue will be treated with CER-001 8mg/kg whatever the randomization arm. A total of 12 infusions will be administered bi-weekly until week 72. A 3T-MRI scan assessing the carotid and femoral artery will be optimally performed at this visit. A final safety visit will occur at week 76, 4 weeks after the last infusion.

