6.2 Protocol deviations

A list of protocol deviations has been written by ICTA PM and sent to the sponsor for approval. The list contains possible protocol deviations (according to inclusion/exclusion criteria, disallowed treatments, minimum treatment exposure, and calendar of visits...), and significant deviations which require immediate information to the Sponsor. This list may be updated in the course of the data management process, and will be finalized during the data review meetings before database lock and unblinding.

TANGO_DeviationsLi

During the data review, the impact of each deviation (minor/major) on the primary endpoint will be discussed and thus, the list of patients to be excluded from the PP population will be defined.

Number and percentage of patients with at least one deviation, at least one major deviation, at least one deviation by type (Entry criteria / Study procedures / Investigational medicinal product) will be described. Each deviation will also be summarized by the number and percentage of patients who experienced it.

6.3 Disposition of patients

The following data will be described:

- Number of screened patients [a]
- Number of screening failures and reasons for screening failures
- Number of randomized patients grouped by treatment
- Number of patients for whom the blind was broken
- Number of patients with ABCA-1, ApoA-1 or both mutations
- Number of patients who did not receive any medication and reason for non-treatment
- Number of patients who received double-blind medication
- Treatment actually received (CER-001/Placebo)
- Number of patients who completed the study
- Number of premature discontinuations of the study treatment and reason for premature discontinuation (at each visit, and overall)
- Number of premature withdrawals and reason for premature withdrawal (at each visit, and overall)
- Number of patients who completed the induction period grouped by treatment (visit at W8 performed)
- Number of patients who completed the maintenance period grouped by treatment (visit at W24 performed)
- Number of patients who completed the extension period grouped by treatment (visit at W48 performed)
- Patient's follow-up duration
- Inclusion date of the first patient (FPFV: First Patient First Visit), date of first visit of the last patient (LPFV) and last visit date of the last patient (LPLV: Last Patient Last Visit)
- Number of patients in each analysis set and reasons for exclusion from the analysis sets

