7.3.2 Treatment compliance

Treatment compliance will be assessed on the mITT population according to randomized treatment group. Compliance (%) with the study treatment will be summarized on each study period (Induction / Maintenance / Extension) and at W24, W48 as follows:

- Compliance during induction phase (%) = Number of infusions totally administered between W0 and W8 / 9 * 100
- Compliance during maintenance phase (%) = Number of infusions totally administered between W10 and W24 / 8* 100
- Compliance during extension phase(%) = Number of infusions totally administered between W26 and W48 / 12 * 100
- Compliance at W24 (%) = Number of infusions totally administered between W0 and W24 / 17
 * 100
- Compliance at W48 (%) = Number of infusions totally administered between W0 and W48 / 29* 100

Average dose, total dose of CER-001 as well as administered dose *vs* expected dose will be summarized at W8, W24, W48, and are defined as follows:

- Total dose at Wi (mg) = $\sum_{v=1}^{ni} CER001$ dose prescription for infusion $v\left(\frac{mg}{kg}\right)$ * Weight at infusion $v\left(kg\right)$ * Actual volume administered at infusion $v\left(mL\right)$ / 250, when n_i = number of infusions received between W0 and Wi
- Average dose at Wi (mg) = Total dose at Wi (mg) / number of infusions received between WO and Wi
- Administered dose vs expected dose at Wi (%) = Total dose at Wi (mg) / (8 * $\sum_{v=1}^{mi} Weight$ at infusion v) * 100, when m_i = number of infusions planned between W0 and Wi

In addition, a by-patient listing will be produced for each patient who verified for at least one visit:

- Dose prescription different from 8 mg/kg
- Time elapsed between study medication infusion preparation and study medication administration > 72h (48h for Canadian sites)
- Start infusion time stop infusion time > 65 min or < 55 min
- Total volume administered = No

For these patients, the listing will include, for all available visits:

- Patient ID, visit, treatment arm
- Dose prescription (mg/kg)
- Date and time of study medication infusion preparation
- Date of infusion, start and stop infusion time
- If not administered, reason
- If infusion duration different from 60 min, reason

CER-001-CLIN-009 CER-001

- Total volume administered (Yes/No)
- If No, volume administered (mL)

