7.5 Safety data

All safety analyses will be performed on the safety population according to the actual treatment received.

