7.5.1 Adverse events (AE)

AE term (Investigator term) will be assigned to the lowest level term (LLT), and a preferred term (PT) will be classified by a high level term (HLT), a high level group term (HLGT) and a system organ class (SOC) according to the Medical Dictionary for Regulatory Activities (MedDRA) thesaurus, version 19.1 or higher.

An adverse event will be considered as treatment-emergent (TEAE) if AE onset date is between first infusion of CER-001 and last infusion of CER-001 + 28 days, or if AE occurred before the first infusion of CER-001 but gets worse on study treatment. In case of incomplete date(s), see section 7.1.4.

An overview of the number of patients with at least one AE and the corresponding number of AEs will be presented including:

- Any AE
- Any TEAE
- Any serious TEAE
- Any severe TEAE
- Any TEAE leading to dose reduction of the study medication
- Any TEAE leading to temporary discontinuation of the study medication
- Any TEAE leading to permanent discontinuation of the study medication
- Any TEAE related to the study medication (Related = definite, probable or possible)
- Fatal AE
- Fatal TEAE
- Any coronary event (Coronary event = event for which HLGT = Coronary artery disorders)

All PT with HLGT = Coronary artery disorders will be described in the same way in a separate table.

CER-001-CLIN-009 CER-001

Note: recurring AEs (*i.e.* AEs classified with the same Preferred Term (PT)) for a given patient will be only counted once and only their most severe intensity or most severe relationship to the study medication will be described.

TEAEs will also be tabulated by System Organ Class (SOC) and PT. They will be presented according to seriousness (Serious / Not serious), severity (Mild/Moderate/Severe) and relationship with the study medication (Related / Not related). They will finally be tabulated by SOC and PT according to relationship with the study medication within severity.

The different analyses described above will be summarized overall, on the induction period and on the post-induction period (AEs that occurred during maintenance or extension phase). Assignment of AEs to periods will be performed as follows:

Period	Assignment
Induction	Start date of TEAE < date of infusion at W10
	(if day of AE is missing then impute to first of the month)
Post-induction	Start date of TEAE ≥ date of infusion at W10
	(if day of AE is missing then impute to first of the month)

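### Exposure and summary adverse-event windows are not closed at the end of double-blind treatment, so open-label CER-001 in former placebo patients may be counted under placebo

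*SAP*

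**What the plan says.** **Exposure.** SAP 7.3.1 defines duration as "Date of last infusion - Date of first infusion + 1) / 7". On grouping it says: "Duration of treatment exposure (weeks) will be described on the safety population according to the actual treatment received". No study period or cut-off is named.

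**Open-label phase.** Protocol 6.6 offers patients who had their week 48 infusion a further 12 infusions, to week 72: "All patients who accept to continue will be treated with CER-001 8mg/kg whatever the randomization arm". Protocol 8.14.3 makes safety over 72 weeks a stated parameter, and Appendix B of the protocol collects adverse events throughout this phase.

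**Safety grouping.** SAP 7.5 states: "All safety analyses will be performed on the safety population according to the actual treatment received". The templates in SAP 12.1 have columns for CER-001, Placebo and Total only.

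**Adverse-event periods.** SAP 7.5.1 summarizes events overall, in induction, and in the "post-induction period (AEs that occurred during maintenance or extension phase". The assignment row for that last period reads only "Start date of TEAE ≥ date of infusion at W10". Elsewhere the SAP ends the extension phase at week 48. The compliance formula in 7.3.2 is "Number of infusions totally administered between W26 and W48 / 12", and the disposition list in 6.3 has "Number of patients who completed the extension period grouped by treatment (visit at W48 performed". The treatment-emergent window in 7.5.1 runs from the first infusion of CER-001 to 28 days after the last.

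**The concern.** A placebo patient who continues has a last infusion at week 72, and that infusion is CER-001. The exposure formula joins the two treatments into one duration. Grouping by treatment received does not settle which column that duration, or an event in week 60, belongs in.

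Safety is a primary objective at 24 weeks and a secondary one at 48 weeks. Protocol section 5 reports that infusion reactions were more frequent with CER-001. With about 10 placebo patients, one patient whose only reaction occurred on open-label CER-001 but who is counted under placebo moves the placebo percentage by 1/10, or 10 points. The open-label data also have no section of their own in the SAP, so no other table would correct the picture.

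**Working it through.** **Inputs.** 30 patients randomized 2:1 (Protocol 6.4), so 20 CER-001 and 10 placebo. Double-blind infusions run from week 0 to week 48 and open-label infusions from week 50 to week 72 (Protocol 6.1, 6.6, Appendices A and B). Nominal visit dates are used.

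**The plan's own figures first.** Protocol 6.1.1 gives a total duration of 68 to 92 weeks. Screening 16 + treatment 48 + follow-up 4 = 68. With the open-label phase, 16 + 48 + 24 + 4 = 92. Infusions: 9 (W0–W8) + 8 (W10–W24) + 12 (W26–W48) = 29, plus 12 open-label (W50–W72). All agree with the documents.

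**Exposure per placebo patient, by the SAP formula.**
- Ending at week 48: (336 + 1)/7 = 48.1 weeks.
- Ending at week 72: (504 + 1)/7 = 72.1 weeks.
- Difference: 24.0 weeks, which is 24.0/48.1 = 50% more than the double-blind time and 24.0/72.1 = 33% of the reported total.

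**Placebo group, if each patient keeps the placebo label.** The documents give no uptake, so the number continuing, n, is an assumption. All 10 are taken to complete double-blind treatment, and all who continue to reach week 72. Mean exposure = 48.14 + 24n/10; open-label share = 2.4n/mean.

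| n continuing of 10 | Mean exposure (weeks) | Share on CER-001 |
|---|---|---|
| 3 | 55.3 | 13% |
| 5 | 60.1 | 20% |
| 8 | 67.3 | 29% |
| 10 | 72.1 | 33% |

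**If the whole patient moves to CER-001 instead.** Each continuing placebo patient then brings 48.1 weeks of placebo time into the CER-001 column.

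**Post-induction adverse-event window.** The upper end here is 28 days after the last infusion.
- Patient who stops at week 48: W10 to W52, 42 weeks.
- Continuing patient under the assignment row as written: W10 to W76, 66 weeks. Of these, W50 to W76 (26 weeks, 26/66 = 39%) fall on or after open-label CER-001.

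**Treatment-emergent window, read literally.** Because it is tied to infusions of CER-001, a continuing placebo patient's window for new-onset events is W50 to W76, which is open-label time only. A placebo patient who does not continue has no such window. Protocol 11.1 instead starts from the first dose of the investigational product.

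**The case against.** **The post-induction period does have an end.** The sentence before the assignment row confines it to maintenance or extension, and the SAP ends extension at week 48. This stands: the row contradicts its introduction, and the period is not simply open-ended. But the protocol also calls the open-label phase the safety extension, so the word alone is not a clean stop. The sentence does nothing for the overall summary or for exposure.

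**A reader might infer that open-label events will be tabulated under placebo and will hide a CER-001 signal.** The documents do not establish this. Table 1 places the treatment received directly after double-blind medication, which suggests one label per patient, but the SAP never says so. Grouping by treatment received could also move the open-label time, or the whole patient, to CER-001. The direction of any distortion is therefore open.

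**The most important events are protected.** SAP 7.5.1 requires individual listings of fatal events, other serious events, and events leading to dose reduction or discontinuation, with the treatment at the time of each event. This stands, and limits the problem to the summary tables.

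**Exposure is a descriptive line.** No exposure-adjusted rate is planned, so duration is not a denominator. Dose and compliance summaries already stop at week 48. Continuing CER-001 patients gain the same 24 weeks. All true; the exposure table would still misdescribe placebo treatment.

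**The SAP may be meant for double-blind data only.** Its objectives omit the 72-week safety objective. Yet SAP 7.4.3 summarizes week 72 imaging by randomized treatment, SAP 10 lists no removal of open-label safety, and Protocol 9.10 locks the database only after the last patient's final visit. The data will be present, and no rule excludes them.

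**Conclusion.** The gap is real and should be closed before unblinding. As written, the exposure formula gives a continuing placebo patient 72.1 weeks under one label, against 48.1 weeks of double-blind treatment. The overall adverse-event summary has no upper bound, and the post-induction row conflicts with its own introduction. The SAP defines neither the period nor the treatment label for open-label exposure and events, so they may be counted under placebo, or placebo time under CER-001.

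Across the placebo group, mean exposure would read between 55.3 weeks (3 of 10 continuing) and 72.1 weeks (all 10), given nominal visit dates, full completion and one placebo label per patient. The all-10 case, 721 against 481 patient-weeks, is an upper bound for an optional phase and not an expected value. The effect on adverse-event percentages cannot be sized from the documents.

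**What to change.** Amend SAP 7.3.1 and 7.5.1, and add a short open-label section:

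1. End double-blind exposure at the last double-blind infusion.
2. Close the double-blind adverse-event window, overall and post-induction, at the first open-label infusion, or 28 days after the last double-blind infusion for patients who do not continue. Align the assignment row with its introduction.
3. Define treatment-emergent events by study drug (CER-001 or placebo) rather than by infusion of CER-001. Without this, closing the windows still leaves double-blind placebo patients with no window for new-onset events.
4. Report open-label exposure and adverse events separately under CER-001, by original arm.

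The cost is a few SAP sentences and one extra set of table columns. The infusion dates and event onset dates needed are already collected.

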7.3.2 Treatment compliance

Treatment compliance will be assessed on the mITT population according to randomized treatment group. Compliance (%) with the study treatment will be summarized on each study period (Induction / Maintenance / Extension) and at W24, W48 as follows:

- Compliance during induction phase (%) = Number of infusions totally administered between W0 and W8 / 9 * 100
- Compliance during maintenance phase (%) = Number of infusions totally administered between W10 and W24 / 8* 100
- Compliance during extension phase(%) = Number of infusions totally administered between W26 and W48 / 12 * 100
- Compliance at W24 (%) = Number of infusions totally administered between W0 and W24 / 17
 * 100
- Compliance at W48 (%) = Number of infusions totally administered between W0 and W48 / 29* 100

Average dose, total dose of CER-001 as well as administered dose *vs* expected dose will be summarized at W8, W24, W48, and are defined as follows:

- Total dose at Wi (mg) = $\sum_{v=1}^{ni} CER001$ dose prescription for infusion $v\left(\frac{mg}{kg}\right)$ * Weight at infusion $v\left(kg\right)$ * Actual volume administered at infusion $v\left(mL\right)$ / 250, when n_i = number of infusions received between W0 and Wi
- Average dose at Wi (mg) = Total dose at Wi (mg) / number of infusions received between WO and Wi
- Administered dose vs expected dose at Wi (%) = Total dose at Wi (mg) / (8 * $\sum_{v=1}^{mi} Weight$ at infusion v) * 100, when m_i = number of infusions planned between W0 and Wi

In addition, a by-patient listing will be produced for each patient who verified for at least one visit:

- Dose prescription different from 8 mg/kg
- Time elapsed between study medication infusion preparation and study medication administration > 72h (48h for Canadian sites)
- Start infusion time stop infusion time > 65 min or < 55 min
- Total volume administered = No

For these patients, the listing will include, for all available visits:

- Patient ID, visit, treatment arm
- Dose prescription (mg/kg)
- Date and time of study medication infusion preparation
- Date of infusion, start and stop infusion time
- If not administered, reason
- If infusion duration different from 60 min, reason

CER-001-CLIN-009 CER-001

- Total volume administered (Yes/No)
- If No, volume administered (mL)

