#### **8.7 Assessments and Procedures for Patients who Prematurely Discontinue Study Medication during double-blind treatment period**

Patients who withdraw from study medication should come to the site for a safety follow-up, 4 weeks after the last dose: the same safety assessments as the ones planned for study completer's week 52 visit (V31) should be performed.

Additionally:

- In case the study medication is stopped prematurely prior to week 24 (V18), a 3T-MRI should be performed as soon as possible after study drug discontinuation. If the patient agrees to stay in the study, he/she will be asked to come back at the site for full assessments as per protocol every 8 weeks until visit V30 and a last 3T-MRI will be performed at visit V30.
- In case the study drug is stopped during the extension treatment period (i.e. after week 24 (visit V18), patient should come back to the site for full assessments as per protocol every 8 weeks until week 48, a last 3T-MRI will be done at week 48.

All AEs (related or not related) must be reported until the final study evaluation at visit V30 and thereafter only the SAEs likely to be related to the study drug or study procedures must be notified.

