6.1 Analysis populations of patients

The statistical analysis will be based on the three populations defined below. To be part of a population, patients should have signed informed consent and fullfill all inclusion / exclusion criteria. Some criteria have been added after the start of the study. Hence patients included before will be considered as compliant to these criteria via a Not Applicable (NA) status.

Safety population

The safety population will comprise all randomized patients who received at least one dose of study medication.

Safety analysis will be performed on the safety population according to the actual treatment received.

Modified Intent-To-Treat (mITT) population

The mITT population will comprise all randomized patients for whom at least one of the following conditions is satisfied:

- 3T-MRI assessment available at baseline (W0) and at least one post-baseline 3T-MRI assessment available
- 18FDG-PET/CT assessment available at baseline (W0) and at least one post-baseline 18FDG-PET/CT assessment available

Per Protocol (PP) population

The PP population will comprise all patients of the mITT population without any major protocol deviations (*Cf.* section 6.3).

Defining study populations and excluding patients from the analysis will be a joint decision taken by Sponsor and ICTA PM' representatives (Statistician and Project Leader). Patients to be excluded and

CER-001-CLIN-009 CER-001

reasons for their exclusion will be discussed during data review meetings, before database lock and unblinding.

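### SAP 7.3.2 summarises compliance (and, by placement, cumulative dose) only in mITT, so a dosed patient who leaves early without a follow-up scan is in no such summary and the figures could be overstated

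*SAP*

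**What the plan says.** SAP 7.3.2 fixes the population for compliance: "Treatment compliance will be assessed on the mITT population according to randomized treatment group". Compliance is the number of complete infusions divided by the number planned: 9 for induction, 8 for maintenance, 12 for extension, 17 to W24 and 29 to W48. The next paragraph introduces further summaries at W8, W24 and W48, beginning "Average dose, total dose of CER-001 as well as administered dose" and going on to the comparison with expected dose. That paragraph names no population.

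SAP 6.1 admits a randomized patient to mITT on either of two conditions: "3T-MRI assessment available at baseline (W0) and at least one post-baseline 3T-MRI assessment available", or "18FDG-PET/CT assessment available at baseline (W0) and at least one post-baseline 18FDG-PET/CT assessment available". The safety set is wider: "The safety population will comprise all randomized patients who received at least one dose of study medication".

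The neighbouring sections use the wider set. SAP 7.3.1 reads "Duration of treatment exposure (weeks) will be described on the safety population according to the actual treatment received", and SAP 7.5 reads "All safety analyses will be performed on the safety population according to the actual treatment received". SAP section 10, which records departures from the protocol, does not explain why 7.3.2 differs.

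**The concern.** Two adjacent exposure subsections describe different sets of patients, grouped in different ways (actual treatment in 7.3.1, randomized group in 7.3.2). Under Protocol 8.3 the first scheduled follow-up MRI is at week 8. Protocol 9.12 foresees patients who withdraw consent, refuse to return and are at most telephoned; one who does so before week 8 has no follow-up scan. That patient counts in the adverse event tables but in no compliance figure and, on the natural reading, in no cumulative-dose figure.

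Safety and tolerability over 24 weeks is one of the two primary objectives. A reader will set the adverse event tables beside the dose tables and assume that they describe the same people. If those missing from the dose tables are mainly early stoppers, treatment looks more completely delivered than it was.

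**Working it through.** **Inputs from the documents.** Planned infusions are 9 + 8 = 17 to W24 and 9 + 8 + 12 = 29 to W48, which agrees with the SAP's denominators. Planned randomization is 30 patients at 2:1, so about 20 on CER-001. The sample-size section allows 20% discontinuation: 24 / 0.8 = 30, as stated. The plan's power figure also reproduces: a two-sample t test with 16 and 8 completers, difference 6.7, SD 4.5 and two-sided 0.05 gives 90.7% against the stated 90%. That figure is not in dispute here.

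**Inputs assumed.** The documents do not say how many dosed patients will lack a qualifying scan pair (k), nor how many infusions each will receive (j). I take j = 1 to 8, because a patient who stops before the W8 visit has had at most 8 infusions. The other CER-001 patients are set at 100%, so the mITT summary shows 100%.

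**Formula.** Mean compliance over all dosed CER-001 patients = [(20 − k) × 100 + k × 100 × j / D] / 20, with D = 9, 17 or 29.

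**One such patient (k = 1).**
- W8: j = 1 gives (1900 + 11.1) / 20 = 95.6%; j = 8 gives (1900 + 88.9) / 20 = 99.4%.
- W24: j = 1 gives (1900 + 5.9) / 20 = 95.3%; j = 8 gives (1900 + 47.1) / 20 = 97.4%. The mITT figure is too high by 2.6 to 4.7 points.
- W48: j = 1 gives (1900 + 3.4) / 20 = 95.2%; j = 8 gives (1900 + 27.6) / 20 = 96.4%. The mITT figure is too high by 3.6 to 4.8 points.

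**Range over k**, all-dosed mean where mITT shows 100%:

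| k | W24 | W48 |
|---|---|---|
| 0 | 100% | 100% |
| 1 | 95.3–97.4% | 95.2–96.4% |
| 2 | 90.6–94.7% | 90.3–92.8% |
| 4 | 81.2–89.4% | 80.7–85.5% |

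The row k = 4 is an extreme: it takes the whole 20% discontinuation allowance and supposes that every one of those patients stopped before W8 and was never rescanned.

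**Administered versus expected dose.** For a patient of constant weight w given j full doses, the ratio at W24 is (8 × w × j) / (8 × w × 17) = j / 17, the same as compliance, so the table carries over.

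**Average dose.** This is total dose divided by infusions received. For the same patient it is (8 × w × j) / j = 8 × w whatever j is. Stopping early at full dose does not bias it; it moves only if the patients left out had reduced or incomplete doses, or a different weight.

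**The opposite direction.** If 19 mITT patients average 90% and one fully dosed patient is excluded for want of a baseline scan, the all-dosed mean is (19 × 90 + 100) / 20 = 90.5%, so mITT understates. Nor does mITT require dosing: a randomized, scanned but never-dosed patient would enter it at 0%.

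**A gap in the formula.** Expected dose sums weight at infusion over all planned infusions. For an infusion that was never given there is no such weight, so the ratio is undefined for exactly the early stoppers at issue. Separately, Protocol 9.6 bases the dispensed amount on weight at Screening, whereas the SAP's dose formulas use weight at each infusion.

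**The case against.** The case against giving this much weight is good, and most of it stands.

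- **The gap is narrow.** Anyone who stops after W8 will normally have the W8 scan. For a stop before week 24, Protocol 8.7 says that "a 3T-MRI should be performed as soon as possible after study drug discontinuation", and Protocol 9.12 says that stopping study drug is not withdrawal from the study. What remains is mainly patients who stop before W8 and then leave. There may be none.
- **Much is reported elsewhere.** The individual listings in SAP 7.5.1 give dose and total infusions for patients with serious events or events leading to dose reduction or discontinuation. SAP 6.3 counts discontinuations with reasons, and SAP 7.7 lists all data. With about 20 active patients, listings are informative. A reader might infer that adverse events cannot be related to dose at all; these listings show otherwise.
- **mITT has a purpose.** Compliance by randomized group in the efficacy set is the right companion to the efficacy result.
- **The population for the dose figures is inferred.** The sentence that names mITT speaks only of compliance.

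What does not stand is that these outputs close the gap. Duration of exposure does not show missed infusions, partial volumes or reduced doses. The by-patient listing in 7.3.2 is triggered by an altered dose, a long delay after preparation, an unusual infusion time or incomplete volume; a patient who has three complete, punctual, full-dose infusions and then leaves need meet none of these. The other listings show patients one by one. No summary of infusions or cumulative dose on the safety population is specified.

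**Conclusion.** The point holds as a minor one. Compliance, total dose and administered-versus-expected dose could be overstated because the set on which they are summarised requires a follow-up scan. On the assumptions above (20 CER-001 patients, the others fully compliant, a stop before W8 with no later scan) the size is about 3 to 5 points at W24 and 4 to 5 at W48 per such patient, and zero if there are none.

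A reader might go further and conclude that the tolerated dose is overstated, always in that direction, and for every dose measure. The documents do not support this. The effect depends on patients whose number is unknown, patients without a baseline scan can push it the other way, and average dose per infusion is untouched by stopping early at full dose. Leaving early is also not the same as intolerance; withdrawn consent is one route. No efficacy test and no adverse event rate is affected.

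**What to change.** In SAP 7.3.2:

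1. Produce compliance, total dose and administered-versus-expected dose on the safety population by actual treatment, matching 7.3.1 and 7.5. The planned-infusion denominators already in the formulas stay as they are.
2. Keep the mITT version by randomized group as the companion to the efficacy results.
3. Name the population for the dose figures.
4. Define which weight the expected-dose formula uses for planned infusions that were not given, and reconcile the SAP's weight at infusion with the weight at Screening in Protocol 9.6. Which one applies is for the sponsor to settle.

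The cost is a few lines of SAP text and a second run of a table that has to be programmed anyway. The reported compliance may turn out less favourable.
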